**Table 2 Criteria for Dose Modification of Chemotherapy Dose**

Toxicity	Grade	Action
Neutropenia	Grade 4	Monitor ANC counts every 3 days until resolved to <Grade 3
Febrile neutropenia	Grade 4	Reduce the next dose of ifosfamide and etoposide by 20%
Mucositis	Repeated grade 3 or Grade 4	Reduce etoposide by 20%
Renal Toxicity	Serum creatinine is 1.5 – 3 × ULN maximum serum creatinine for age and gender	Interrupt ifosfamide and etoposide for 1 week
Hematuria	>50 RBC/ high power field (hpf)	Interrupt ifosfamide for 1 week
Neurological Toxicity	≥ Grade 2	Interrupt and reduce ifosfamide and etoposide each by 20% of the previous dose. After 2 dose reductions, subject must discontinue the chemotherapy drugs, but if benefiting, can continue on single-agent lenvatinib at the investigator's discretion

ANC = absolute neutrophil count, RBC = red blood cell, ULN = upper limit normal.

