##### 9.5.1.4.1 ADVERSE EVENTS

An AE is any untoward medical occurrence in a patient or clinical investigation subject administered an investigational product. An AE does not necessarily have a causal relationship with the medicinal product. For this study, the study drugs are lenvatinib, ifosfamide, and etoposide.

The criteria for identifying AEs in this study are:

- Any unfavorable and unintended sign (including an abnormal laboratory finding), symptom, or disease temporally associated with the use of an investigational product, whether or not considered related to the investigational product (Note: Every sign or symptom should not be listed as a separate AE if the applicable disease [diagnosis] is being reported as an AE)
- Any new disease or exacerbation of an existing disease. However, worsening of the primary disease should be captured under efficacy assessments as PD.
- Any deterioration in nonprotocol-required measurements of a laboratory value or other clinical test (eg, ECG or x-ray) that results in symptoms, a change in treatment, or discontinuation of study drug
- Recurrence of an intermittent medical condition (eg, headache) not present pretreatment (Baseline)
- An abnormal laboratory test result should be considered an AE if the identified laboratory abnormality leads to any type of intervention, withdrawal of study drug, or withholding of study drug, whether prescribed in the protocol or not

All AEs, regardless of relationship to study drug or procedure, should be recorded beginning from the time the subject signs the study ICF through the last visit and for 30 days after the subject's last dose. Refer to [Section 9.5.4.1](#) for the time period after the end of treatment for SAE collection.

Abnormal laboratory values should not be listed as separate AEs if they are considered to be part of the clinical syndrome that is being reported as an AE. It is the responsibility of the investigator to review all laboratory findings in all subjects and determine if they constitute an AE. Medical and scientific judgment should be exercised in deciding whether an isolated

laboratory abnormality should be classified as an AE. Any laboratory abnormality considered to constitute an AE should be reported on the Adverse Event CRF.

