**Table 4 Clinical Laboratory Tests**

Category	Parameters
Hematology	Hematocrit, hemoglobin, platelets, RBC count, and WBC count with differential (bands, basophils, eosinophils, lymphocytes, monocytes, neutrophils)
Chemistry	
Electrolytes a	Bicarbonate, chloride, potassium, sodium, calcium, magnesium, phosphorus
Liver function tests	ALT, alkaline phosphatase, AST, conjugated (direct) bilirubin b , total bilirubin, INR/PT, aPTT/PTT c
Renal function tests	BUN or urea, creatinine
Other chemistries	Albumin, amylase, glucose, LDH, lipase, total protein
Thyroid function tests d	Thyroid stimulating hormone, free T4 level
Urinalysis for microscopy e	RBCs
Urine dipstick testing e,f	Blood, protein, glucose
Other g	Pregnancy test (serum or urine $\beta$ -hCG)

ALT = alanine aminotransferase, aPTT = activated partial thromboplastin time, AST = aspartate aminotransferase, BUN = blood urea nitrogen,  $\beta$  hCG = beta-human chorionic gonadotropin, INR = International Normalized ratio, LDH = lactate dehydrogenase, aPTT = activated partial thromboplastin time, RBC = red blood cells, T4 = thyroxine, TSH = thyroid stimulating hormone, WBC = white blood cells.

- a. Electrolytes such as potassium, calcium, and magnesium should be monitored and abnormalities, when considered clinically significant, should be corrected in all participants before starting treatment.
- b. Direct bilirubin should be assessed if total bilirubin is elevated.
- c. INR/PT and aPTT/PTT should only be performed as part of the screening assessment. During the study, INR/PT and aPTT/PTT should be performed if clinically indicated.
- d. Thyroid function will be assessed every 2 cycles for all subjects.
- e. If urine dipstick testing suggests a urinary tract infection, or if clinically indicated, a urine microscopy, culture, and sensitivity should be performed at the institution's laboratory
- f. If urine protein is  $\geq 2+$ , then a spot test for protein-creatinine ratio and if possible, a 24-hour urine collection should be done to quantify the 24 hour urine protein excretion.
- g. For sites in Germany: HIV and Hepatitis B/C tests are required during Screening.

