All clinical laboratory tests during the study will be performed at qualified local laboratories. All hematology, blood chemistry (including pregnancy test, as applicable), and urinalysis samples are to be obtained prior to study drug administration and sent to the local laboratory on the day of collection unless otherwise instructed.

Clinical chemistry and hematology results must be reviewed prior to administration of study drug on Cycle 1 Day 1 and within 48 hours after dispensing study drug for all subsequent cycles. Electrolytes such as potassium, calcium, and magnesium should be monitored and

abnormalities, when considered clinically significant, should be corrected in all participants before starting treatment. Scheduled assessments may be performed within 72 hours prior to the visit. If  $\geq$  Grade 3 hematologic or clinical chemistry toxicity, repeat laboratory test and AEs assessment at least every 3 days (until improvement to  $<$  Grade 3). Refer to [Table 1](#) (study drug dose reduction and interruption instructions) for the management of clinically significant laboratory abnormalities. Every effort should be made to collect samples for analysis at the local laboratory at the same time.

A laboratory abnormality may meet the criteria to qualify as an AE as described in this protocol (see [Section 9.5.1.4.1](#) and the CRF Completion Guidelines. In these instances, the AE corresponding to the laboratory abnormality will be recorded on the Adverse Event CRF (see [Section 9.5.4.3.2](#)).

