- l. Clinical chemistry and hematology results must be reviewed by the investigator prior to administration of study drug on C1D1 and within 48 hours after administering any study drug for all subsequent cycles. Electrolytes such as potassium, calcium, and magnesium should be monitored and abnormalities, when considered clinically significant, should be corrected in all participants before starting treatment. Scheduled assessments may be performed within 72 hours prior to the visit. If  $\geq$ Grade 3 hematologic or clinical chemistry toxicity, repeat laboratory test and AEs assessment at least every 3 days (until improvement to <Grade 3). TSH should be assessed for all subjects. For sites in Germany: HIV and Hepatitis B/C tests are required during Screening.
- m. Urine dipstick testing should be performed at Screening, Baseline, C1D15, C2D1, C2D15, and Day 1 of every subsequent cycle, or more frequently as clinically indicated, and at the Off-treatment Visit. For subjects with a history of proteinuria  $\geq$ 2+, urine dipstick testing should be performed until the results have been 1+ or negative for 2 treatment cycles. If a new event of proteinuria  $\geq$ 2+ occurs, refer to [Section 9.4.1.1.4](#) for further management guidelines. Urine glucose should be performed as part of the urine dipstick.
- n. Sampling (one 2 mL sample per time point) for PK analysis of lenvatinib will be performed (in subjects in Arm A only) on Cycle 1 Day 1 at 0.5 to 4 hours and 6 to 10 hours postdose, on Cycle 1 Day 15 at predose, 0.5 to 4 hours and 6 to 10 hours postdose, and on Cycle 2 Day 1 at predose. All predose samples are to be drawn approximately 24 hours following the dose administered on the previous day. If dose interruption is necessary at these time points, please contact the sponsor. Pharmacokinetic sampling should not be performed for any subject with a body weight <13 kg (please see [Section 9.5.1.3.1](#)).

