**Table 6 Schedule of Assessments in Study E7080-G000-230 – Extension Phase**

Phase	Extension a	
Period	Treatment Period a	Follow-up Period
Visit	98	99
Cycle	Cycle X +1 and beyond	Off-Tx Visit
Day	1	
Procedures/Assessments		
Pregnancy test b	X	X
Lansky play score/ Karnofsky PS c	X	X
Physical examination d	X	X
Vital signs e	X	X
12-lead ECG f	As clinically indicated	
Echocardiogram or MUGA scan g	As clinically indicated	
Clinical chemistry and hematology h	X	X
Urine dipstick testing i	X	X
Study treatment j	Arm A: Lenvatinib+ifosfamide+etoposide a Arm B: Ifosfamide + etoposide a	
Tumor assessments: CT/MRI k	After data cutoff for the primary analysis, tumor assessments may be performed as clinically indicated as per the institutional guidelines (but no less frequently than every 12 weeks), following the prevailing local standard of care.	
Brain CT/MRI l	After data cutoff for the primary analysis, tumor assessments may be performed as clinically indicated as per the institutional guidelines, following the prevailing local standard of care.	
Height m	To be checked every 4 cycles	X
Tanner Stage n		X
HRQoL o	X	X
Proximal Tibial growth plate x-ray p		X
Dental examinations q	X	X
Survival r	X	X
Concomitant medications s	Throughout	X
AEs/SAEs t	Throughout	X

AE = adverse event, CT = computerized tomography, ECG = electrocardiogram, HRQoL = Health-Related Quality of Life, ICL = imaging core laboratory, MRI = magnetic resonance imaging, MUGA = multiple-gated acquisition, PD = disease progression, PS = performance status, SAE = serious adverse event.

- a. In the Treatment Period, subjects still on study treatment following the completion of the Randomization Phase will continue to receive study treatment as outlined in [Section 9.1.2.1](#) until disease progression, development of unacceptable toxicity, subject request, withdrawal of consent, or discontinuation of study by the sponsor, whichever occurs first.
- b. A serum or urine pregnancy test will be performed on Day 1 of each cycle and at the Off-treatment Visit in women of childbearing potential.
- c. A Lansky play score or Karnofsky performance status score will be obtained at Day 1 of every cycle visit.

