**Table 6 Schedule of Assessments in Study E7080-G000-230 – Extension Phase**

Phase	Extension a	
Period	Treatment Period a	
Visit	98	99
Cycle	Cycle X +1 and beyond	Off-Tx Visit
Day	1	

symptom-directed physical examination will be performed at any time as clinically indicated.

- e. Assessments will include vital signs (resting BP, HR, RR, and body temperature), and weight. Blood pressure that is consistently above the 95th percentile for sex, age, and height/length for subjects <18 years old; or BP  $\geq$ 140/90 mmHg for subjects  $\geq$ 18 to 25 years old requires further evaluation. Refer to hypertension management guidelines in [Section 9.4.1.1.2](#).
- f. Single 12-lead ECG. Subjects must be in the recumbent position for a period of 5 minutes prior to the ECG.
- g. An echocardiogram or MUGA scan is to be performed as clinically indicated.
- h. Clinical chemistry and hematology results must be reviewed within 48 hours after administering any study drug for all subsequent cycles. Electrolytes such as potassium, calcium, and magnesium should be monitored and abnormalities, when considered clinically significant, should be corrected in all participants before starting treatment. Scheduled assessments may be performed within 72 hours prior to the visit. If  $\geq$ Grade 3 hematologic or clinical chemistry toxicity, repeat laboratory test and AEs assessment at least every 3 days (until improvement to <Grade 3). TSH should be assessed for all subjects.
- i. Urine dipstick testing should be performed on Day 1 of every cycle, or more frequently as clinically indicated, and at the Off-treatment Visit. For subjects with a history of proteinuria  $\geq$ 2+, urine dipstick testing should be performed until the results have been 1+ or negative for 2 consecutive cycles. If a new event of proteinuria  $\geq$ 2+ occurs, refer to [Section 9.4.1.1.4](#) for further management guidelines. Urine glucose should be performed as part of the urine dipstick.
- j. Subjects randomized to Arm A will continue to receive lenvatinib only until progressive disease, unacceptable toxicity, or withdrawal of consent.
- k. After data cutoff for the primary analysis, tumor assessments may be performed as clinically indicated as per the institutional guidelines (but no less frequently than every 12 weeks), following the prevailing local standard of care. The scans will no longer be required to be sent to the ICL.

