- i. Clinical chemistry and hematology results must be reviewed by the investigator prior to administration of study drug on C1D1 and within 48 hours after administering any study drug for all subsequent cycles. Electrolytes such as potassium, calcium, and magnesium should be monitored and abnormalities, when considered clinically significant, should be corrected in all participants before starting treatment. Scheduled assessments may be performed within 72 hours prior to the visit. If  $\geq$ Grade 3 hematologic or clinical chemistry toxicity, repeat laboratory test and AEs assessment at least every 3 days (until improvement to <Grade 3). TSH should be assessed for all subjects.
- j. Urine dipstick testing should be performed at Baseline, C1D15, C2D1, C2D15, and Day 1 of every subsequent cycle, or more frequently as clinically indicated, and at the Off-treatment Visit. For subjects with a history of proteinuria  $\geq$ 2+, urine dipstick testing should be performed until the results have been 1+ or negative for 2 treatment cycles. If a new event of proteinuria  $\geq$ 2+ occurs, refer to [Section 9.4.1.1.4](#) for further management guidelines. Urine glucose should be performed as part of the urine dipstick.
- k. A serum or urine pregnancy test will be performed at the Baseline Visit (or within 72 hours prior to the first dose of study medication), on Day 1 of each cycle from Cycle 2 onwards, and at the Off-treatment Visit in women of childbearing potential.
- l. Subjects on optional lenvatinib crossover treatment will continue to receive lenvatinib until disease progression, development of unacceptable toxicity, subject request, or withdrawal of consent, whichever occurs first. If the sponsor terminates the study, the sponsor will provide study drug(s) (outside of the study) for subjects who have not met the criteria for study drug discontinuation.
- m. All subjects who receive suspension formulation, with the exception of subjects using a nasogastric or gastrostomy tube, must complete the Palatability Questionnaire on C1D1 (or the subsequent visit). If the subject is unable to complete the questionnaire this must be done by their parents or their legal guardian.

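### From Cycle 2, outside Germany, the laboratory review window lets at least 2 of 3 daily ifosfamide/etoposide doses precede required sight of a creatinine at which Table 2 interrupts both drugs

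*Protocol*

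**What the plan says.** The protocol sets the timing of laboratory review in four places.

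- **Table 5 footnote l** (Randomization Phase): the investigator reviews results before dosing on Cycle 1 Day 1, and afterwards "within 48 hours after administering any study drug for all subsequent cycles".
- **Table 7 footnote i** (optional crossover): the same two-part rule, with review before dosing "on C1D1 and within 48 hours after administering any study drug for all subsequent cycles".
- **Table 6 footnote h** (Extension Phase): no pre-dose review at all. It reads "Clinical chemistry and hematology results must be reviewed within 48 hours after administering any study drug for all subsequent cycles". The study treatment row of that table still lists "Arm A: Lenvatinib+ifosfamide+etoposide".
- **Section 9.5.1.4.3**: review before dosing on Cycle 1 Day 1, then "within 48 hours after dispensing study drug for all subsequent cycles". The clock starts at dispensing here, not at administration.

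The rule is not confined to lenvatinib. Section 9.5.1.4.1 states: "For this study, the study drugs are lenvatinib, ifosfamide, and etoposide". The chemistry panel in Table 4 includes renal function ("BUN or urea, creatinine"). In Table 2, a creatinine of 1.5 to 3 times the maximum for age and gender carries the action "Interrupt ifosfamide and etoposide for 1 week".

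Section 9.5.1.4.3 also requires samples to be taken before study drug is given and sent to the local laboratory the same day. It allows scheduled assessments up to 72 hours before the visit. For German sites, Appendix 11 strikes out the 48-hour allowance and requires investigator review before study drug is administered.

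**The concern.** Table 2 works only if someone has seen the creatinine before the infusion starts. From Cycle 2 the review rule does not require that. A site could draw the sample on time, give chemotherapy on Day 1 and Day 2, look at the result within the permitted window, and be compliant with the review rule throughout, even though the result called for both drugs to be held.

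What is at stake is subject safety in a trial that enrolls from age 2. The protocol itself treats kidney damage from ifosfamide as a known risk: exclusion criterion 14 bars subjects with previous Grade 3 or worse ifosfamide-related nephrotoxicity. The endpoint, sample size and primary analysis do not depend on this point.

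**Working it through.** The protocol gives no figure of its own on this point, so there is none to reproduce. The check counts doses against the review deadline and then looks for text that closes the gap.

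**Inputs**
- Ifosfamide 3,000 mg/m²/day and etoposide 100 mg/m²/day on Days 1, 2 and 3 of a 21-day cycle, for at most 5 cycles (Section 9.4.1).
- Review deadline from Cycle 2: 48 hours (the four places above).
- Assumption: daily doses at about the same hour, so at 0, 24 and 48 hours from the first.

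**Doses before the deadline, per course**

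| Clock starts at | Deadline, hours from Day 1 dose | Doses strictly before | Doses at or before |
|---|---|---|---|
| Day 1 dose (footnotes) | 48 | 2 of 3 | 3 of 3 |
| Day 2 dose | 72 | 3 of 3 | 3 of 3 |
| Day 3 dose | 96 | 3 of 3 | 3 of 3 |
| Dispensing 24 h before Day 1 (illustration for 9.5.1.4.3) | 24 | 1 of 3 | 2 of 3 |

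Under the *administering* wording the minimum is 2 of 3:
- Ifosfamide: 2 × 3,000 = 6,000 of 3 × 3,000 = 9,000 mg/m².
- Etoposide: 2 × 100 = 200 of 3 × 100 = 300 mg/m².

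**Over Cycles 2 to 5**
- Chemotherapy days: 4 × 3 = 12.
- Days that can precede required review: 4 × 2 = 8 of 12, or 12 of 12 if the Day 3 dose falls at or before the deadline.
- Cycle 1 is left out because pre-dose review is required there.

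**With review before Day 1 dosing:** 0 of 3 doses per course.

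**Does other global text close the gap?**
- Section 9.4.1.2 asks for close monitoring of blood counts before the next chemotherapy cycle. It does not name creatinine.
- Sections 9.1.2.1 and 9.4.1 foresee chemotherapy being withheld on Day 1, but do not say which results must be seen to decide that.
- Table 5 footnote l asks for clinically significant electrolyte abnormalities to be corrected before treatment starts. Its examples are potassium, calcium and magnesium.
- Section 9.5.1.4.3 fixes when the sample is drawn, not when its result is read.
- Section 9.4.2.2 refers administration to local prescribing information, which is not at hand.

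None of these expressly requires the creatinine to be seen first. The German text does, and the same drugs, doses and Table 2 action apply elsewhere. Appendix 11 does not name Table 5 footnote l, but it cites Section 9.5.2.1, which contains Table 5.

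**The case against.** The strongest reply is that 48 hours is an outer limit for review, not an instruction to treat without results. The surrounding text assumes a decision on Day 1: a fresh sample is mandatory, local laboratories process it, and chemotherapy can be held until recovery. Section 9.4.1.2 also directs sites to the product labelling for managing ifosfamide and etoposide toxicity, and that labelling may require renal function to be checked first. Table 2 is itself presented as guidance, and its action is a one-week interruption, not permanent discontinuation.

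Most of this stands, and it limits the point. Many sites will look before dosing. If the labels require it, what remains is that the protocol is looser than the label and should be brought into line. But a stated rule that accepts later review still conflicts with the purpose of Table 2.

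Some stronger readings are tempting, and the documents do not support them:
- *Dosing rests on a creatinine up to three weeks old.* The preceding scheduled chemistry is about 21 days old at Day 1 of Cycles 4 and 5. However, Section 9.5.1.4.3 requires a new pre-dose sample each time. The gap is in the deadline for reading it.
- *All four places allow at least 2 of 3 doses.* This holds for the three footnotes. Under *dispensing*, drug handed out a day early leaves only 1 dose strictly before the deadline.
- *A count of courses measures harm.* Multiplying subjects by cycles counts courses under the rule, not late reviews or raised creatinines.
- *The Extension Phase is a large source of exposure.* Enrollment is planned for 20 months and the primary analysis for about month 32. That leaves 12 months after the last entry, against 5 × 3 = 15 weeks of chemotherapy. Table 6 would reach chemotherapy only if cutoff came much earlier, and its footnote j describes Arm A as continuing on lenvatinib only.

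**Conclusion.** The point holds as a conflict between the review window and the renal action in Table 2. For sites outside Germany, the three footnotes allow at least two thirds of the daily doses in a course to be given before a creatinine that calls for interruption must be seen.

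This assumes that review is left to the end of the permitted window, that daily doses are about 24 hours apart, and that local prescribing information does not require earlier review. The 8 of 12 figure further assumes that a subject receives all five cycles under Table 5. The protocol gives no rate of creatinine at 1.5 to 3 times the maximum, so the number of subjects affected cannot be estimated. This is a cheap improvement to a safety rule; it does not threaten the trial's result.

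**What to change.** In Section 9.5.1.4.3, Table 5 footnote l, Table 6 footnote h and Table 7 footnote i:

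- Require the investigator to review chemistry and hematology before the Day 1 chemotherapy of every chemotherapy cycle.
- Keep the 48-hour window only for cycles in which lenvatinib is given alone. This is less strict than the German rule, which removes the window altogether.
- Use *administering* in all four places, so that the clock has one starting point.

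The cost is wording in the next amendment. Because pre-dose sampling is already required, no extra blood draw is needed. The downside is an occasional short delay on Day 1 while a result is awaited, which local laboratories and sampling up to 72 hours before the visit should keep small.
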